### ***10.4. Records Retention***

Data (electronic and paper) will be stored in a secure location until study analysis and publication completion, after which any linkage to PHI will be destroyed. Anonymized microbial nucleic acid sequence data and associated metadata will be uploaded on public databases (i.e., the National Center for Biotechnology Information's Sequence Read Archive) as required by funding agencies.

## **11. Study Monitoring, Auditing, and Inspecting**

### ***11.1. Study Monitoring Plan***

This study will be monitored according to the data safety monitoring plan. The investigator will allocate adequate time for such monitoring activities. The Investigator will also ensure that the monitor or other compliance or quality assurance reviewer is given access to all the above noted study-related documents and study related facilities (e.g. pharmacy, diagnostic laboratory, etc.), and has adequate space to conduct the monitoring visit.

### ***11.2. Data Quality Assurance***

During monitoring visits, the monitor will review CRFs to ensure data accuracy, completeness, and clarity, including laboratory reports and other subject records with the stipulation that subject confidentiality will be strictly maintained in accordance with local and federal regulations, including HIPAA requirements. Instances of missing or uninterruptible data will be resolved in coordination with the Investigator.

### ***11.3. Auditing and Inspecting***

The investigator will permit study-related monitoring, audits, and inspections by the EC/IRB, the sponsor, government regulatory bodies, and University compliance and quality assurance groups of all study related documents (e.g. source documents, regulatory documents, data collection instruments, study data, etc.). The investigator shall notify the Sponsor of all audits and inspections by regulatory bodies. The investigator will ensure the capability for inspections of applicable study-related facilities (e.g. pharmacy, diagnostic laboratory, etc.). Participation as an investigator in this study implies acceptance of potential inspection by government regulatory authorities and applicable University compliance and quality assurance offices.

## **12. Ethical Considerations**

This study is to be conducted in accordance with applicable US government regulations and international standards of Good Clinical Practice, and applicable institutional research policies and procedures.

This protocol and any amendments will be submitted to a properly constituted independent Ethics Committee (EC) or Institutional Review Board (IRB), in agreement with local legal prescriptions, for formal approval of the study conduct. The decision of the EC/IRB concerning the conduct of the study will be made in writing to the investigator and a copy of this decision will be provided to the sponsor before commencement of this study.

Protocol modifications, except those intended to reduce immediate risk to study subjects, may be made only by the University of Pennsylvania and the Sponsor. A protocol change intended to eliminate an apparent immediate hazard to subjects may be implemented immediately, provided the IRB/IEC is notified within 5 days.

Any permanent change to the protocol must be handled as a protocol amendment. The written amendment must be submitted to the IRB/IEC and the investigator must await approval before implementing the changes. The Sponsor will submit protocol amendments to the appropriate regulatory authorities for approval.

### ***12.1. Risks***

The main risks of this study are related to administration of the investigational product. The most severe possible risks include: allergic reaction, donor-derived infection, aspiration (for upper gastrointestinal administration), bowel perforation (for lower gastrointestinal administration), and death. Other risks include: nausea, vomiting, abdominal pain, diarrhea, flatulence, fever. Product specific risks are described in [Section 9.1.4](#).

Theoretical long-term risks may include: changes in metabolism, weight changes, development of autoimmune conditions.

Other risks include loss of privacy or confidentiality, as a result of study staff interacting with subjects.

These risks will be discussed with subjects during the informed consent process. The eligibility criteria will help mitigate these risks (e.g., excluding subjects with neutropenia or bowel perforation, and not permitting subjects at risk for aspiration to receive investigational product via upper gastrointestinal delivery). To minimize the risk of privacy and confidentiality loss, the minimum number of required study staff will interact with subjects, and all collected data will be protected as above.

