### **3.1.6. Allocation to Interventional Group**

Stratified randomization will be performed based on severity category (severe versus severe complicated) in a 2:1 fashion (two to the FMT intervention (PMT-001, 002, or 003) and one to the standard of care control group). The randomization schedule will be prepared using a random-size block strategy to ensure balance throughout the trial. Prior to enrollment of the first subject, a randomization table will be produced for each category using Stata statistical software and the “Ralloc” package.

[figure not shown]
If subjects are known to have enteral access (either actively receiving capsule medications and/or nutrition by mouth or via pre-existing enteric tube, as prescribed by the clinical care team), they will undergo a second randomization in a 1:1 fashion between allocation to FMT by enema (i.e., PMT-001) or FMT by upper enteral administration (i.e., PMT-002 or PMT-003). Subjects who are randomized to FMT but who lack enteral access or who are deemed to have ileus (i.e., enteral medications and nutrition held) by the clinical care team will receive PMT-001 enema. Subjects who are randomized to FMT but have bowel discontinuity will only be eligible for the intervention arm that coincides with their presumed side of CDI (e.g. if CDI in residual rectum/colon, only eligible for PMT-001). Prior to enrollment of the first subject, a randomization table will be produced for the second (route of administration) randomization using R statistical software.

Subjects randomized to receive FMT, and then to receive FMT via upper delivery will have the decision made between PMT-002/PMT-003 according to how other medications and nutrition are being delivered (i.e., those receiving nutrition and medications via enteric tube will receive PMT-002 suspension, and those eating food and receiving oral medications will receive PMT-003 capsules). Cross-over between PMT-002 and PMT-003 will be permitted if repeat FMT administration is indicated, but a subject’s mode of nutrition and medication administration has changed. Cross-over between PMT-001 and PMT-002/003 will be permitted if repeat FMT administration is indicated, but a subject has lost enteral access and is unable to tolerate oral medications.

For a graphical representation of the allocation to the interventional groups, refer to [Figure 1](#).

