#### 4.2. Exclusion Criteria

1. Evidence of colon/small bowel perforation at the time of study screening.
2. Goals of care are directed to comfort rather than curative measures.

3. Moderate (ANC < 1000 cells/uL) or severe (ANC < 500 cells/uL) neutropenia.
4. Known food allergy that could lead to anaphylaxis.
5. Pregnancy
  - a. For subjects of childbearing potential (ages 18 to 55), the subject must have a negative urine pregnancy test within 48 hours of consent and no more than 48 hours prior to first product administration.
6. Receipt of FMT or enrollment in a clinical trial for FMT within the last 3 months.
7. COVID-19 infection, as defined by a positive nucleic acid or antigen test within the prior 14 days and symptoms consistent with COVID-19 infection

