### 5.2. Intervention Regimen

This study is a randomized, controlled, open label trial. Subjects will be screened to evaluate if they meet inclusion criteria for severe or severe complicated/fulminant CDI. If eligible, subjects will participate in the informed consent process. Following informed consent, subjects will be randomized to one of three arms: (1) standard of care antibiotics (no intervention), (2) PMT-upper GI administration plus standard of care antibiotics, or (3) PMT-lower GI administration plus standard of care antibiotics. In the intervention arms, subjects will then be eligible to receive up to two additional administrations of PMT (upper or lower GI) at 3-day intervals if they do not meet pre-defined criteria for clinical improvement for 24 hours (see [Section 2.1](#)). If PMT administration is unable to be performed on the scheduled days (3-day intervals), administration within 1 calendar day before or after those days will be permitted. Subjects will be assessed for eligibility for an additional dose on the day of repeat administration. Subjects will be followed until 180 days after their last PMT dose.

During the intervention period, following informed consent and randomization ([Section 3.1.2](#)), subjects in either intervention arm (not the standard of care control arm) will receive single-dose PMT administration, with PMT formulation determined per randomization. Administration of the product is described in [Section 5.7](#) below. Subjects will be eligible to receive up to two additional administrations of PMT (per same randomization) at 3 days and 6 days (+/-1 day) after the initial dose if they fail to meet criteria for clinical improvement ([Section 3.2.1](#)) and as long as they do not have bowel surgery. Antibiotics prescribed as part of routine clinical care for CDI will not be altered by the intervention.

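### Section 12.1 bars subjects at risk for aspiration from the upper GI route, but the route rules in 3.1.6, 6.1.4 and 5.7 screen for that risk only by proxy

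*Combined protocol and SAP*

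**What the plan says.** Section 12.1 names aspiration, for upper administration, among the most severe possible risks. It says the eligibility criteria help to reduce the risks and gives as one example "not permitting subjects at risk for aspiration to receive investigational product via upper gastrointestinal delivery".

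Route is decided in 3.1.6. Enteral access means "either actively receiving capsule medications and/or nutrition by mouth or via pre-existing enteric tube, as prescribed by the clinical care team". For subjects allocated to FMT who have such access, "they will undergo a second randomization in a 1:1 fashion between allocation to FMT by enema" or by the upper route. "Subjects who are randomized to FMT but who lack enteral access or who are deemed to have ileus", with intake held, receive the PMT-001 enema. Subjects with bowel discontinuity may receive only the route that matches the presumed site of CDI. Within the upper route, the product follows current intake: "those receiving nutrition and medications via enteric tube will receive PMT-002 suspension", and those eating and taking oral medication receive PMT-003 capsules.

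Section 6.1.4 reviews enteral access to decide who qualifies for the route randomization. Section 5.7 makes PMT-002 conditional on a tube already in place, and a gastric tube qualifies.

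For repeat doses, 3.1.6 allows a switch between PMT-001 and the upper products only when "a subject has lost enteral access and is unable to tolerate oral medications". Section 5.2 provides for "additional administrations of PMT (per same randomization) at 3 days and 6 days". Sections 3.1.2, 3.1.4 and 6.2.4 each word the repeat-dose route differently.

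**The concern.** Section 12.1 states a restriction on route for a risk that the protocol itself ranks among the gravest. Staff who follow 3.1.6 and 6.1.4 exactly can still arrive at an assignment that 12.1 rules out. They would then have to give the dose against 12.1 or override the allocated route on the spot, an intentional departure of the kind 7.9.1 calls an exception.

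What is at stake is subject safety and the accuracy of what ethics reviewers are told. The favourable assessment in 12.3 rests on the risks and benefits set out just before it. Aspiration monitoring (3.1.3, 3.2.3.1, 9.1.3) begins once the dose has been given, so it can detect aspiration but cannot stand in for a restriction on who receives the upper route.

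**Working it through.** There is no planned figure to reproduce. The check sets the statement in 12.1 beside each rule that decides route.

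**First dose**

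| Section | What is tested | Does it ask about aspiration risk? |
|---|---|---|
| 6.1.4 | Enteral access, listed before randomization (6.1.5) | No |
| 3.1.6 | Prescribed oral or tube intake | Indirectly, through the decision to feed |
| 3.1.6 | No access, or ileus with intake held: enema | Indirectly |
| 3.1.6 | Bowel discontinuity: route by site of CDI | No |
| 5.7 | Tube already in place for PMT-002 | No |

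Take a subject judged at risk for aspiration whose team nevertheless continues tube feeding or oral intake, with no ileus and an intact bowel. The subject has enteral access under 3.1.6, passes 6.1.4 and, if allocated to FMT, is randomized 1:1 on route. If upper is drawn, a tube-fed subject receives PMT-002 and an eating subject PMT-003. Every step follows the protocol, and the result is what 12.1 says is not permitted.

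**Repeat doses**

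- 3.1.2 permits whichever route is clinically appropriate. On its face this leaves room to avoid the upper route.
- 3.1.4 keeps the formulation from the initial randomization.
- The 3.1.6 cross-over to PMT-001 needs both lost access and intolerance of oral medication. Aspiration risk alone does not qualify.
- 5.2 holds to the same randomization.
- 6.2.4 allows a change of formulation, on reassessment of how nutrition and medication are given.

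So one statement gives latitude, one allows change on a different ground, and the rest restrict it.

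**Size**

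The documents give no frequency of aspiration risk. At the first dose the number affected lies between 0 and the 30 subjects planned for the upper arm (4.5).

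**Effect of redirecting at-risk subjects**

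Planned FMT total: 30 + 30 = 60, against 30 controls (4.5). Suppose k of the 60 are sent straight to enema, and assume everyone else has enteral access and an intact bowel. Expected numbers are:

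- upper: (60 − k)/2
- lower: k + (60 − k)/2 = (60 + k)/2
- sum: (60 − k)/2 + (60 + k)/2 = 60

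On average, every two subjects redirected cost the upper arm one subject. The pooled FMT group used in the primary analysis (8.5.2) stays at 60 against 30 for any k.

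**The case against.** The best defence is that 12.1 loosely summarizes 3.1.6 and that the treating team's decision to feed is the aspiration screen. The proxy is substantial: intake must be prescribed by the care team, subjects without access or with ileus go to enema, and tube-fed subjects are dosed through their tube. The care team can also object before enrollment (3.1.1, 4.3, 6.1.3), a licensed clinician gives each dose (5.7), and the investigator may withdraw a subject for safety (6.6).

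Much of this stands, and it rules out several stronger readings.

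- A reader might infer that the trial has no protection against aspiration before dosing. The proxy shows otherwise.
- A reader might infer that the fault is a missing entry criterion, since the perforation example in 12.1 matches "Evidence of colon/small bowel perforation at the time of study screening" in 4.2 and the neutropenia example is there too. But a limit on route would not normally sit among the entry criteria: a subject at risk for aspiration can still be a control or receive the enema.
- A reader might infer that no repeat-dose rule allows a safer route. Section 3.1.2 gives some latitude.
- A reader might infer that no safeguard exists anywhere. Figure 1 is not shown, so the claim is limited to the text available, although 3.1.6 describes that figure as a picture of the same allocation.

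What the defence does not answer is the difference between having access and being free of aspiration risk. Feeding is prescribed for routine nutrition and medication. The study dose is up to 152 mL of suspension or up to 32 capsules over 10 to 90 minutes, and nowhere is the team asked to judge aspiration risk for that load. The team's chance to object comes before the route is known. Withdrawal for safety is not a rule for choosing the route.

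**Conclusion.** The concern holds in a limited form. Section 12.1 states a restriction that the route rules, as written in the text available, apply only by proxy. The gap is the subject at risk for aspiration whose team continues oral or tube intake. That subject can be allocated to PMT-002 or PMT-003 in full compliance with 3.1.6.

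How many subjects this concerns cannot be estimated from the documents. The conclusion assumes only that some at-risk patients are still fed, and that Figure 1 adds no rule beyond the text it illustrates. It would be wrong to infer a threat to the primary analysis or its power: the problem concerns route within FMT, and the pooled comparison does not change. This should be corrected as a safety inconsistency with a cheap remedy.

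**What to change.** Add one item to the enteral-access check in 6.1.4, and refer to it in 3.1.6: does the clinical care team consider this subject at risk for aspiration with upper delivery? If yes, the subject, if allocated to FMT, receives PMT-001 in the same way as a subject without enteral access. Because the check is listed before randomization, the answer is fixed before allocation is known, which matters in an open-label trial.

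For repeat doses, add aspiration risk to the 3.1.6 cross-over rule as a reason to switch to PMT-001, and refer to that rule in 3.1.4, 5.2 and 6.2.4. No new entry criterion is needed.

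The cost is one line on an existing check and wording in five sections (3.1.4, 3.1.6, 5.2, 6.1.4 and 6.2.4), with no new visit or test. The downside is somewhat fewer upper-route subjects, by a number the documents do not allow one to estimate. The item relies on the care team's judgment rather than a formal definition, so broad use of it would enlarge that loss.

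Minimum alternative: if the sponsor regards the feeding decision as sufficient, reword 12.1 to describe the enteral-access and ileus rule. That removes the inconsistency but leaves the safety gap.

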### ***12.2. Benefits***

Potential direct benefits include: cure or improvement of CDI symptoms more quickly than with standard of care, reduction in risk of complications of CDI (death, need for surgery), reduction in risk of recurrence of CDI, which have been suggested by observational studies to date (Table 1). Indirect benefits include contributing to medical knowledge about the utility of FMT in this study population and therefore helping patients who have this disease in the future.

### ***12.3. Risk Benefit Assessment***

Based on the risks and benefits outline above, the benefits of this study outweigh the potential risks. This is a patient population with significant illness at high risk for complications, and the investigational products are likely to reduce this risk. While there are potential adverse outcomes associated with this product, prior studies have demonstrated that the risk of these occurring is relatively low.

### ***12.4. Informed Consent Process / HIPAA Authorization***

Informed consent must be obtained before any of the baseline procedures are performed. The consent process will occur in the setting of the potential subject's regularly scheduled clinical care or by telephone after referral from the potential subject's clinical care team. Written informed consent will be obtained whenever possible. In cases where COVID-19 isolation status or visitor policies preclude an in-person consent process, verbal consent will be obtained utilizing a witnessed consent. This will be then documented in both the electronic health record and the data collection system. An explanation of the trial and discussion of the possible risks and discomforts will be given by the Investigators and/or study staff. Only those potential subjects who fulfill all eligibility criteria will be entered into the trial. Informed consent will take place as an ongoing dialogue between the Investigator/study staff and subjects during the entire duration of their participation. Potential subjects that are unable to read the study consent and/or

do not have the opportunity to take home and review with family/friends or do not present in the clinic with a family member will have the consent read to them by a study team member in the presence of a non-partial person that will verify the consent has been read in full to the patient. Privacy will be preserved by minimizing the number of study staff in contact with the potential subject. Coercion will be avoided by clearly stating that declining to participate will not affect clinical care. The informed consent and HIPAA authorization will be documented on paper, and completed paper records will be scanned for digital storage on secure university servers.

### **13. Study Finances**

#### **13.1. Funding Source**

Program support from PennMedicine, Department of Medicine, and Centers for Disease Control and Prevention (CDC) U54CK000485.

#### **13.2. Conflict of Interest**

All University of Pennsylvania Investigators will follow the University of Pennsylvania Policy on Conflicts of Interest Related to Research.

#### **13.3. Subject Stipends or Payments**

There are no subject payments or stipends.

### **14. Publication Plan**

The investigator is responsible for authoring a final clinical study report and sharing with the sponsor team. The Clinical Study Report will be issued within 12 months of data lock and the results summary will be posted to [clinicaltrials.gov](http://clinicaltrials.gov) as required by legal agreement, local law, or regulation. A manuscript will be progressed for publication in the scientific literature if the results provide important scientific or medical knowledge. This study will be published by the principal investigator, [name].

